273 This will be a 12-week randomized, double-blind, placebo-controlled interventional study
274 in 40 patients with T2DM and CAD with an acceptable glycemic control on their current
275 diabetes regimen who require elective coronary artery bypass grafting (CABG) regardless
276 of their participation in the study.

277 A minimum time frame of 3-week treatment will be considered to detect significant
278 changes in the study endpoints. If not all subjects would be able to complete the 12
279 weeks, study outcomes will be evaluated at the 3 week time point.

280

281 **Study Design** Study subjects will be randomized in two groups of 20 patients to receive
282 additional liraglutide, (L-group) or to remain on current treatment or placebo (D-group).

- 283 • L-group will be started on liraglutide. Liraglutide will be started and administered
284 for 12 weeks prior to CABG with a starting dose of 0.6 mg (after a least one week)
285 and subsequent increments to 1.2 mg (after a least one week) and to 1.8 mg (after
286 at least a week on 1.2 mg). The dose of 1.8 mg daily will be maintained until the
287 end of the 12-week study. Other and current diabetes treatment will be continued.
288 In those study participants who may be impacted by CABG scheduling and
289 COVID-19, and cannot complete the 12-week treatment, we will consider a
290 minimum time frame of 3 weeks to detect significant changes in the study primary
291 endpoints.
- 292 • D-group: placebo will be administered in addition to current treatment prior to the
293 CABG with a starting dose of 0.6 mg (after a least one week) and subsequent
294 increments to 1.2 mg (after a least one week) and to 1.8 mg (after at least a week
295 on 1.2 mg). Patients will be started on a supervised diet to achieve approximately
296 5% of weight loss between 3 and 12 weeks. In those study participants who may be
297 impacted by CABG scheduling and COVID-19, and cannot complete the 12-week
298 treatment, we will consider a minimum time frame of 3 weeks to detect significant
299 changes in the study primary endpoints.

300

301 Ultrasonographic measurement of EAT thickness will be performed at baseline and
302 after 12 weeks in all patients, regardless of the study arm.

303 All groups will receive lifestyle and diabetes education, and supervised diet as
304 part of the standard care, to insure similar glycemic control between arms and
305 weight loss. Study patient will be also required to check and log their finger stick

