307 blood glucose twice daily (fasting before breakfast and at bedtime) and report the
308 readings to the study coordinator on a bi-weekly base.
309

310 **Rationale for study Design**

311 The randomized, double-blind, placebo-controlled study design will allow for an
312 independent and unbiased effect of liraglutide on study results.
313

314

315 **Rationale for minimum study time line of 3 weeks.**

316 The pre-operative clinic schedule may not always allow to wait the full 12 weeks between
317 the patient's enrollment and the CABG, standard of care procedure. [name] is the only
318 cardiac surgeon at UM performing elective CABGs. Once the patient is randomized and
319 randomly allocated to one of the study arms, the length of the treatment is set by the date
320 of standard of care CABGs. During the current COVID-19 pandemic, the number of
321 elective CABGs has been reduced and we cannot reschedule or delay the surgery
322

323 **Study Population:** Study group will be formed by 40 patients with T2DM and with
324 clinically and angiographically stable CAD who will undergo CABG surgery, as part of
325 their standard medical care. Cardiac surgery will be elective procedure in
326 hemodynamically stable patients taking their standard cardiac treatments and under the
327 care of the cardiologist.

328

329 **Study team and site:** [name] is Professor of Medicine, Division of
330 Endocrinology, Diabetes and Metabolism. [name] pioneered EAT echocardiographic
331 measurement and he is considered the leading expert in the epicardial fat. [name] will
332 lead and supervise liraglutide therapy, EAT measurement, analysis and interpretation of
333 the data. [name], Research Assistant Professor, Dept. Microbiology and Immunology,
334 will lead and supervise adipose tissue analysis. [name] is associate professor
335 of Cardiology and contributes to patient recruitment. [name], professor of
336 cardiothoracic surgery will be the cardiac surgeons for this study. Low calorie diet (LCD)
337 and other nutritional aspects will be managed and supervised by the Division of
338 Endocrinology registered dietitian (RD), as part of the standard care. University of Miami
339 has been the site of several National Health Institute (NIH) studies and many peer-reviewed
340 publications. The Division of Endocrinology Diabetes and Metabolism is fully equipped
341 and trained to visit, follow up and manage patients with diabetes. The Division of

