380 methods (as required by local law or practice)

381

382 **Investinational drug**

383 Liraglutide [rDNA origin] injection, solution for subcutaneous use. Liraglutide will be
384 prescribed according to the same, current indications of the marketed Victoza.

385

386 **Withdrawal Criteria**

387 1. The subject may withdraw at will at any time.
388 2. The subject may be withdrawn from the trial at the discretion of the investigator due to
389 a safety concern or if judged non-compliant with trial procedures or included in
390 contravention to the inclusion and/or exclusion criteria.
391 3. Subject diagnosed with acute pancreatitis by clinical and/or radiographic criteria.
392 4. Pregnancy, positive pregnancy test prior to the enrollment or intention to become
393 pregnant.
394 5.
395 6. Subjects who will not tolerate liraglutide dose increase to 1.2 or 1.8 mg will remain in
396 the study at the highest tolerated dose

397 **Subject Replacement**

398 There will be no replacement of subjects in this trial.

399

400 **Rationale for Study Population**

401 We anticipate that approximately 400 patients will be screened in a 2-year period. We will
402 recruit patients with T2DM and clinically and angiographically stable CAD who will
403 undergo CABG surgery, as part of their standard medical care. Cardiac surgery will be
404 elective procedure in hemodynamically stable patients taking their standard cardiac
405 treatments and under the care of the cardiologist.

406

407 **Recruitment strategy:** Participants will be recruited among the outpatient population who
408 routinely refer to the Division of Cardiothoracic Surgery ([name] and collaborators),
409 Division of Cardiology ([name]) and Division of Endocrinology, Diabetes and
410 Metabolism outpatient clinics ([name]), at University of Miami.

411 **Visit Procedures**

412 **Study Timetable:** This study will consist of two clinical visits prior the cardiac surgery
413 and adipose tissue collection during the surgical intervention. Consecutive subjects with
414 T2DM and CAD who are candidate for elective cardiac surgery regardless of their
415 participation in the study will be selected, informed and consented. Patients suitable to
416 wait 12 weeks for cardiac surgery will be identified by the cardiology team and accordingly
417 scheduled, as part of the standard care. Anthropometrics, blood draw for laboratory
418 measures and echocardiographic measurements of EAT thickness will be performed at

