419 baseline and before cardiac surgery that will be scheduled 12 weeks after study enrollment
420 and treatment. Adipose tissue collection will be collected during the cardiac surgery.
421 Study outcomes will be collected at 3 weeks in both groups in those patient who may not
422 be able to complete the 12- week treatment due to CABG logistics and COVID-19 impact
423 on scheduling

424

425 **Assessments for Efficacy**

426 **Adipose tissue collection:** EAT biopsy samples (average 0.5-1.0 g) will be taken, before
427 heparin administration, near the proximal tract of the right coronary artery. Each tissue
428 sample will be snap frozen in liquid nitrogen and stored at -80 °C until analysis in a freezer.
429 The subcutaneous fat tissue (SAT) will be harvested at the site of the thoracic wound and
430 preserved in the same manner.

431 **Gene expression:** in freshly isolated mature adipocytes (from EAT and SAT), extraction
432 of total RNA, quantification of mRNA, c-DNA generation qRT-PCR will be performed for
433 measuring expression of the inflammatory genes (TNF- α , IL-6) and GLP-1R.

434 **Western Blot:** Total proteins will be extracted from frozen EAT and SAT adipocytes and
435 blotted for TNF- α , IL6, as previously described.

436 In addition to the mRNA expression of GLP1R, we will also measure protein expression
437 of GLP-1R by western blotting. Total cell lysates from the EAT will be obtained as follows.
438 Cells will be resuspended in M-PER (Mammalian Protein Extraction Reagent, Thermo
439 Scientific), incubated on ice for 20 min, sonicated for a few seconds and then centrifuged
440 (14,000 rpm, 15 min, 4°C) to obtain protein lysates which will be stored at -80°C until
441 use. Protein content will be determined by Bradford assay before western blotting runs.
442 Antibodies will be anti-GLP1R Mab 3F52 (Novo Nordisk) and anti-GAPDH (GeneTex)
443 as loading control.

444 **Immunofluorescence**

445 To confirm GLP-1R protein expression, immunofluorescence will be performed on EAT
446 and SAT samples using Mab 3f52 against GLP-1R, as previously described by Pyke et al
447 23-24. This mouse monoclonal antibody has been extensively validated to show its
448 specificity. Due to the relatively low abundance of GLP-1R the immunofluorescence will
449 be performed using a tyramide signal amplification reagent (TSA kit#26 from Molecular
450 probes) according to the manufacturer instructions. In summary, cryosection of the samples

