480 correlation coefficient. Inter- and intra-observer reproducibility will be evaluated by the
481 intra- class correlation coefficient in all subjects. Echocardiograms will be read by Dr
482 [name] and an experienced cardiac imaging technician. Previously published studies
483 have shown that intra- and inter-observer reproducibility of epicardial fat measurement was
484 excellent. Intra-class correlation coefficients varied from 0.90 to 0.98 and from 0.93 to
485 0.98, respectively indicating good reproducibility and reliability. Both readers will be
486 blinded to the subjects' clinical data.

487 **Anthropometrics and Clinical measures:** As standard of care, height (in cm) and weight
488 (in kg) will be measured, and BMI will be calculated. Waist circumference (in cm or
489 inches) will be measured as the minimum circumference between the lower rib margin and
490 the iliac crest. Blood pressure will be also measured.

491 **Blood Measurements:** Lipid panel, lipase, and amylase are not study end-points and will
492 be collected if made available through a standard of care procedure at baseline and after 4
493 or 12 weeks.

494 **Low calorie Diet (LCD)** A low calorie diet program will be prescribed to study patients
495 and controls. A RD who will reach out to patients to insure adherence to the dietary
496 program will supervise the LCD. This will help patients to achieve approximately 5% of
497 weight loss between 3 and 12 weeks.

498 **Assessments for Safety**

499 **Potential Risks to the Subjects**

500 The risks of this study are minimal are mainly related to risks associated with the
501 investigational drug liraglutide, echocardiogram, blood draw, and a potential breach of
502 confidentiality.

503 **Drug therapy:** liraglutide, (Victoza®), is a GLP-1A indicated as an adjunct to diet and
504 exercise to improve glycemic control in adults with T2DM. Liraglutide is taken once daily
505 at any time of day, without regard to the timing of meals. Liraglutide is injected

506 subcutaneously in the abdomen, thigh, or upper arm. Liraglutide may cause mild and
507 usually well-tolerable gastro-intestinal side effects (5%), such as nausea, constipation.
508 Liraglutide is contraindicated in patients with a personal or family history of medullary
509 thyroid cancer and in patients with Multiple Endocrine Neoplasia (MEN). Based on
510 spontaneous postmarketing reports, acute pancreatitis has been observed in patients treated

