541 identifying information. All data used in the analysis and reporting of this evaluation will
542 be without identifiable reference to the patient. Data used for reports or publications will
543 never include identifiable information such as name, date of birth, social security number,
544 address, or medical record number and in most cases will not include any identifiers other
545 than sex, age, race, and diagnosis.

546 **Scheduling CABG timing**

547 In patients with stable CAD found to have CAD anatomy that requires CABG, the timing
548 and schedule for revascularization will be determined by [name]. Patients suitable to
549 wait between 3 and 12 week- period for revascularization will be identified and managed
550 with optimal medical therapy, and scheduled for complete revascularization with CABG.

551 **Managing patients becoming unstable or developing acute events during the study**

552 The inclusion and exclusion criteria will limit the possibility of recruiting patients with
553 unstable CAD/angina, as defined before. Study patients showing unstable angina or
554 developing acute cardiac events will be transferred promptly to the local emergency
555 department for evaluation and treatment. If patient status becomes acute and emergent, the
556 adverse event will be reported to the IRB.

557 **Unblinding**

558 The investigator will follow the study's randomization procedures. The blind should
559 ordinarily be broken for serious and unexpected adverse experiences that are associated
560 with the use of a drug to determine if there is a reasonable possibility that the experience
561 may have been caused by the drug. Certain adverse events such as ***known consequences***
562 ***of the underlying disease under investigation*** or events common in the study population
563 generally should ***not*** require unblinding.

564 We feel that in the not likely case (given the inclusion criteria) that a study patient will
565 become unstable or develop acute events during the study, this event would more likely
566 fall in the ***known consequences of the underlying disease under investigation*** rather than
567 caused by the study drug, and therefore should ***not*** require premature unblinding.
568 Nevertheless, it will be upon the principal investigator's best judgement and discretion to

569 break the blind. In this case, the principal investigator will promptly document and report
570 to the IRB and Novo Nordisk any premature unblinding.

571

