
(i) The investigation is not intended to be reported to FDA as a well-controlled study in support of a new indication for use nor intended to be used to support any other significant change in the labeling for the drug;
	
Meets criteria. This clinical trial is not intended to be reported to the FDA in support of a new indication or change in Victoza labeling.

(ii) If the drug that is undergoing investigation is lawfully marketed as a prescription drug product, the investigation is not intended to support a significant change in the advertising for the product.
	
Meets criteria. This investigation is not intended to support a significant change in the Victoza advertising.

(iii) The investigation does not involve a route of administration or dosage level or use in a patient population or other factor that significantly increases the risks (or decreases the acceptability of the risks) associated with the product
	
Meets criteria. In this clinical trial liraglutide (and the matching placebo) will be administered according to the labeled route and dosage (Pre-filled, multi-dose pen for subcutaneous injection that delivers doses of 0.6 mg, 1.2 mg, or 1.8 mg (6 mg/mL, 3 mL). In this clinical trial liraglutide (and the matching placebo) will be used according to the indications. Liraglutide will be used in adults with type 2 diabetes (T2DM) in adjunct to diet and exercise advices and not as first-line therapy, as study patients will continue their standard diabetes therapy. Hence, liraglutide/placebo is prescribed under inclusion criteria that are the same as for marketed Victoza. Exclusion criteria for liraglutide are also the same as marketed Victoza. This investigation will not increase the risks in the study population.

(iv) The investigation is conducted in compliance with the requirements for institutional review set forth in part 56 and with the requirements for informed consent set forth in part 50;
	
Meets criteria. This study will be reviewed and approved by the University of Miami IRB Institutional Review board prior to study start and will meet with the requirements for informed consent.

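### The protocol does not say whether the trial or usual care sets the CABG date, and it neither names nor assesses waiting for surgery as a study risk

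*Combined protocol and SAP*

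**What the plan says.** Three parts of the protocol tie surgery to the study.

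- Study Design gives liraglutide "for 12 weeks prior to CABG with a starting dose of 0.6 mg".
- The Study Timetable, under Visit Procedures, says that patients suitable to "wait 12 weeks for cardiac surgery will be identified by the cardiology team and accordingly" scheduled. It describes this as standard care.
- The same section puts the second set of measurements before an operation counted from enrolment: "baseline and before cardiac surgery that will be scheduled 12 weeks after study enrollment".

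The rationale for the 3-week minimum ties the study to surgery instead. After a patient is "randomly allocated to one of the study arms, the length of the treatment is set by the date" of the standard-of-care operation. It adds that, during the pandemic, the number of "elective CABGs has been reduced and we cannot reschedule or delay the surgery".

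The section on scheduling CABG timing refers to patients suitable to "wait between 3 and 12 week- period for revascularization will be identified and managed" medically until surgery. Study Design and the Study Timetable add a fallback of at least 3 weeks for patients who cannot complete 12 weeks because of surgical scheduling or COVID-19.

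On risk, the section on potential risks opens with "The risks of this study are minimal are mainly related to risks associated with the" study drug, echocardiogram, blood draw and confidentiality. It goes on to discuss tissue collection. The answer to exemption criterion (iii) under Regulatory Considerations ends: "This investigation will not increase the risks in the study population".

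**The concern.** These patients have coronary disease that requires bypass surgery. If joining the trial can lengthen the wait for that surgery, the wait is a consequence of participation and belongs in the risk assessment. If it cannot, the protocol should say so plainly. As written, it supports either answer.

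There is also an analytic stake. The epicardial tissue for the primary endpoint can be taken only at operation, so the CABG date fixes both the length of exposure and the time of assessment. Statistical Considerations plans to adjust the gene-expression analysis for time in patients who do not complete 12 weeks. If the date can move after allocation, observed duration is a post-randomisation variable that may respond to tolerability or cardiac events. Adjusting for it could then bias the treatment comparison.

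**Working it through.** No figure in the plan needs reproducing here. The check is a comparison of the sections.

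**1. What anchors the surgery date?**

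| Section | Anchor | Wait or treatment length |
|---|---|---|
| Study Design (liraglutide group) | Treatment course | 12 weeks, minimum 3 if scheduling or COVID-19 intervenes |
| Study Timetable | Enrolment and treatment | 12 weeks, with outcomes at 3 weeks for those who cannot complete |
| Rationale for 3-week minimum | Standard-of-care CABG date | Whatever that date allows |
| Scheduling CABG timing | Clinical judgement of suitability to wait | 3 to 12 weeks |

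The first two rows run from trial to surgery. The third runs from surgery to trial. The fourth gives a range without saying what selects a point within it.

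**2. Does any section settle the conflict?** Take, for illustration only, a patient whose usual-care slot would fall at week 4.

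- Under the Study Timetable's main rule, surgery is at week 12.
- Under the rationale section, surgery is at week 4 and treatment lasts 4 weeks.
- Under the fallback, the answer depends on whether an available earlier slot counts as being unable to complete 12 weeks. The text does not say.
- Under the scheduling section, either date lies within the range.

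The rules agree for a patient whose usual-care date is already 12 weeks after enrolment. They do not yield one rule for a patient who could be operated on earlier.

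**3. Is the wait assessed as a risk?**

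- Potential risks: drug, echocardiogram, tissue collection, blood draw and confidentiality are discussed. Waiting is not.
- Protection against risks: telephone contact every 2 weeks, pregnancy testing and privacy measures. Waiting is not mentioned.
- Patients who become unstable: emergency transfer and an IRB report. The unblinding section then judges such events more likely to reflect the underlying disease than the drug. It does not consider time spent waiting as a study-related contributor.
- Exemption criterion (iii): the answer covers route, dose, indication and eligibility, then makes a general statement of no increased risk. Waiting is not mentioned.

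**4. Is the planned duration fixed before allocation?** The rationale section says the CABG date sets treatment length once the patient is randomised. It does not say that the date was assigned before randomisation, and the protocol provides no record of an assigned date or of later changes. The time adjustment therefore has no stated pre-randomisation duration to use.

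**The case against.** The best defence is that the sections describe a 12-week target with a 3-week minimum. On that reading, the scheduling section simply states the range, and the fallback covers anyone whose surgery comes sooner. This is a fair reading of the permitted length, and the 3-to-12-week wording need not be a separate contradiction. It still does not say whether the trial or usual care chooses the date.

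Other points stand in part.

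- The Study Timetable calls its scheduling standard care, and patients need CABG whether or not they take part. So the text does not establish that the trial sets the date. But the label does not explain why usual care would count from study enrolment, and needing surgery does not settle when it happens.
- The statement that surgery cannot be moved sits in a sentence about the pandemic. The sentence before it, on what sets treatment length, has no such limit.
- The risk list is introduced as the main risks, not all of them. Unstable disease is excluded and acute events have a management plan. The fair charge is that waiting is not named or assessed, not that acute events are ignored.
- Criterion (iii) chiefly concerns risks associated with the product, so the regulatory point is secondary. It arises because the criterion also reaches other risk-increasing factors and the answer is a blanket statement.
- Consent pages are not in the available copy, so what patients are told about waiting cannot be judged.

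A reader might infer that two different parties decide the date, because the cardiology team identifies who can wait and one individual determines timing. These are different tasks and the individual's name has been removed, so no conflict can be shown.

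**Conclusion.** The inconsistency is real and should be corrected: the current text does not say which date governs, and the wait is not assessed as a study risk. This rests on the wording alone and needs no outside figure.

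Its clinical size cannot be stated. A reader might infer that the trial delays surgery, and might multiply the 12 − 3 = 9 week span by 40 patients to get 360 patient-weeks of extra waiting. The documents do not support this. Three weeks is a minimum treatment period, not a usual-care wait, and nothing shows that any patient is held back. With no event rate given, an extra-event count would be an assumption throughout. Nor do the documents show the risk statement or the exemption claim to be false. Each lacks an assessment of the wait, which matters if the trial can influence the date.

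The analytic concern is conditional in the same way. It applies if the date can change after allocation, which the protocol neither rules out nor tracks.

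**What to change.** 1. Reconcile Study Design, the rationale for the 3-week minimum, the Study Timetable and the section on scheduling CABG into one statement of which date governs. The choice of rule is for the clinical team; none is proposed here.
2. Record the clinically assigned CABG date before randomisation, and any later change with its date and reason. Base the planned time adjustment on the pre-randomisation planned duration rather than the observed one.
3. If the trial can influence the date, name the wait under potential risks and revisit the general statement in the answer to criterion (iii). Tabulate acute cardiac events before surgery by arm from the adverse event data already collected from consent onward. Because both arms wait, this table cannot measure the effect of waiting. It shows whether events that could move the date differ between arms.

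The cost is protocol wording, one pre-randomisation form field with a change log, and one table from existing data. The downside is a less favourable risk statement that may need IRB review.

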451 will be performed at -35 °C with 12 μ m thickness using a Leica CM1850 UV cryostat
452 (Wetzlar, Germany). The sections will be fixed for 20 min with 4% PFA, washed with PBS
453 and dried at room temperature overnight. Sections will be washed 3 x with PBS and
454 incubated with PBS with 3% BSA and 0.4% triton X for 1 hour. Sections will then
455 incubated with Mab 3f52 (1:50 dilution) antibody overnight in PBS with 3% BSA and
456 0.4% triton X. Sections will be then washed 4 times with PBS and incubated with
457 biotinylated anti mouse IgG for 1 hour at room temperature, washed 4 times with PBS,
458 then incubated at room temperature with horseradish peroxidase-streptavidin for another
459 hour, washed 4 times with PBS and then incubated at room temperature with alexa fluor
460 647 tyramide for 10 min. Sections will be further washed 3 times and incubated with DAPI
461 (Thermo fisher, Waltham, MA) for 30 min. The samples will be washed 3 times with PBS
462 and mounted on Mowiol 4-88 (Sigma-Aldrich, St Louis, MO). The tyramide signal can
463 amplify from 10 to 200 times the immunofluorescence signal from low expressed proteins
464 (Molecular probes, Eugene, OR). The fluorescence images will be acquired using a Zeiss
465 LSM 710 confocal microscope (Oberkochen, Germany).

466 **Echocardiographic EAT Thickness:**

467 Echocardiogram for EAT thickness measurement will be performed at baseline and after
468 12 weeks in all patients, regardless of the study arm. EAT thickness will be measured
469 according to the method firstly described and validated by [name] ⁷⁻⁸. Briefly, EAT will
470 be identified as the echo-free space between the outer wall of the myocardium and the
471 visceral layer of pericardium. EAT thickness will be measured perpendicularly on the free
472 wall of the right ventricle at end-systole in three cardiac cycles. Parasternal long views
473 allow the most accurate measurement of EAT on the right ventricle, with optimal cursor
474 beam orientation. Maximum epicardial fat thickness will be measured at the point on the
475 free wall of the right ventricle along the midline of the ultrasound beam, perpendicular to
476 the aortic annulus, used as anatomical landmark for this view. The average value of three
477 cardiac cycles will be considered.

478 ***Reliability of echocardiographic measurement of EAT***

479 Reliability of echocardiographic measurement of EAT will be assessed by the intra-class

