 632 example, a EAT thickness of 10 mm may likely decrease to 8.5 mm after 3 weeks of
 633 treatment with liraglutide, a clinically meaningful change for the patient cardio-metabolic
 634 profile.

635

636 This sample size also considers the difficulties with recruitment in the real world clinics.
 637 Based on our previous studies in humans, some participants may be lost to follow-up.

638

639 Student's t-test or non-parametric (Mann-Whitney) tests, depending on whether the genes
 640 mRNA expression and protein present or not a normal distribution, will be used to compare
 641 the effects of treatment (liraglutide versus placebo) on the variables measured. Student's
 642 t-test will be also used to compare ultrasound measured EAT thickness before and after
 643 treatments. Continuous variables will be considered as age-adjusted, sex-adjusted and
 644 weight-adjusted means with their SDs or median, if values are skewed.

645 Univariate regression models will be performed to assess the correlation between clinical
646 variables, including echocardiographic EAT thickness and blood tests, and EAT gene and
647 protein expression. Two-tailed $p < 0.05$ indicates statistical significance.

648

649 **Data Handling and Record Keeping**

650 Each of the dedicated clinic exam rooms provides direct access to the clinical research
651 study electronic data capture (EDC) eVelos system provided by the Clinical Research
652 Informatics and Data Management Unit of the Center for Health Informatics and
653 Bioinformatics at University of Miami (UM). The investigator and research coordinator
654 will collect and manage the data.

655 Data collection records with personal identifiers will be stored in locked file cabinets, at
656 [name]. Blood samples drawn
657 and stored in conjunction with this study will not be labeled with information that could
658 directly identify study subjects. Presentation of the study results at scientific meetings or
659 in publications will not identify subjects. Access to research and confidential records will
660 be limited to clinical investigators, research coordinators, and the IRB at UM.

661 **Adipose tissue samples storing**

662 Each adipose tissue sample will be snap frozen in liquid nitrogen and stored at -80°C until
663 analysis in a freezer, in [name] lab, University of Miami, Dept of Microbiology, 1600

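### Echo reading is not stated to be masked to visit or reading order, so the before-versus-after test of EAT thickness (a secondary endpoint) is open to reader expectation

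*Combined protocol and SAP*

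**What the plan says.** - **Reader masking.** Under Reliability of echocardiographic measurement of EAT, the scans have two readers ("Echocardiograms will be read by" a doctor, name removed, and an experienced imaging technician). Both are "blinded to the subjects' clinical data". Nothing is said about visit, scan date, reading order, or whose value is analysed.
- **Timing.** Under Echocardiographic EAT Thickness, scans are taken at baseline and after "12 weeks in all patients, regardless of the study arm".
- **Roles.** Under Study team and site, one team member will "lead and supervise liraglutide therapy, EAT measurement, analysis and interpretation of" the data. The same paragraph says that this person "pioneered EAT echocardiographic" measurement.
- **Test.** Under Statistical Considerations, a Student's "t-test will be also used to compare ultrasound measured EAT thickness before and after" treatment. The sentence before it is more general and applies a t-test or Mann-Whitney test to "the effects of treatment (liraglutide versus placebo) on the variables measured".
- **Hypothesis and power.** Study Hypotheses states the EAT question between arms: a larger fall on liraglutide than on standard therapy. The EAT power text opens with a between-arm difference and later speaks of a before-after difference on liraglutide.
- **Allocation.** Randomization and Blinding describes a double-blind, placebo-controlled, parallel-group trial.

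**The concern.** Allocation blinding protects a comparison of arms. It does not protect a comparison of visits, because a reader can know that a scan is the follow-up without knowing the arm. EAT thickness is measured by placing a cursor on an image, so it leaves room for judgement. The protocol also states a strong prior: Study Rationale describes a large, fast fall in EAT thickness on liraglutide, and the power text gives 10 mm falling to 8.5 mm after 3 weeks as its example. A reader sharing that expectation could read follow-up scans slightly thin, and the whole shift would enter the before-after test.

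High inter-observer agreement would not reveal this. Two readers with the same expectation can agree closely and both be shifted.

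What is at stake is the credibility of the EAT thickness result. The primary endpoint, measured on surgical tissue, is not affected.

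**Working it through.** **1. The plan's own figure.** Inputs from the EAT power table and text: SD 2 mm, difference 1.9 mm (20% of 9.6 mm), two-sided alpha 0.05, 80% power.

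- Two-sample size: n = 2 × (1.96 + 0.84)² × 2² / 1.9² = 17.4, so 18 per arm. With attrition at the 10% ceiling, 18 / 0.9 = 20, the planned number.
- With 20 per arm, noncentral t power is 83.3% for 1.9 mm and 99.3% for 2.88 mm. The plan states 80% and above 99%.

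The stated power therefore reproduces as a between-arm calculation. A paired calculation needs a visit-to-visit correlation, which the plan does not give. For 1.92 mm in 20 patients it gives 82% to 99% as that correlation runs from 0 to 0.5, so the power figure alone does not settle which contrast is meant.

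**2. Assumptions for the bias check (not in the documents).**

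- Reader shift at follow-up: 0.5 mm, with 0.25 mm as a milder case.
- Correlation r between visits: 0.5, 0.7 or 0.8, with SD 2 mm at both visits.
- No true change.

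Is 0.5 mm credible? It is a quarter of the 2 mm that the plan calls clinically significant. The cited intra-class correlations start at 0.90 (intra-observer) and 0.93 (inter-observer). Measurement error = SD × √(1 − ICC), so 2 × √0.10 = 0.63 mm and 2 × √0.07 = 0.53 mm. At the lower end of the cited reliability, a 0.5 mm shift lies within reading noise.

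**3. Formulas.**

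- SD of change = 2 × √(2(1 − r)).
- Before-after test, n = 20, df 19, critical t 2.093: noncentrality = shift × √20 / SD of change.
- Between-arm test on change, 20 per arm, df 38, critical t 2.024: noncentrality = shift difference between arms / (SD of change × √(2/20)).
- False-positive rate = probability that the noncentral t exceeds the critical value in either direction.

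**4. Results for a 0.5 mm shift.**

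| r | SD of change (mm) | Before-after: noncentrality | Before-after: rate | Shift in one arm only: noncentrality | Between-arm: rate |
|---|---|---|---|---|---|
| 0.5 | 2.00 | 1.118 | 18.6% | 0.791 | 12.0% |
| 0.7 | 1.55 | 1.443 | 27.8% | 1.021 | 16.9% |
| 0.8 | 1.26 | 1.768 | 38.9% | 1.250 | 23.0% |

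A 0.25 mm shift gives 8.3%, 10.5% and 13.4% for the before-after test.

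**5. The same shift in both arms.** The difference between arms is 0.5 − 0.5 = 0, so the between-arm test keeps its 5% level. A simulation of 40,000 trials with shifts of 0.5 and 1.0 mm and SD of change 1.5 and 2.0 mm gave 4.9% to 5.1%.

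**The case against.** The best defence is that the trial is double-blind with placebo, the EAT hypothesis is between arms, the power text opens with a between-arm difference, and the general test sentence compares liraglutide with placebo. For that contrast a common reader shift cancels. This stands, and it means that the 19% to 39% range belongs to the before-after test alone. It does not remove the point, because before against after is the only test that the plan ties by name to EAT thickness.

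The route into the arm comparison is also narrow on the protocol's own figures. Weight loss and glucose control are to be kept similar between arms, so they should be poor clues to allocation. Gastrointestinal effects are put at 5%, about 1 patient in 20. A 0.5 mm shift in one patient moves the arm mean by 0.5 / 20 = 0.025 mm. The 12% to 23% range assumes a shift in every patient of one arm and is best read as an upper illustration.

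A reader might infer that the investigator supervising therapy reads the scans, so that the stated blinding is already broken. The documents do not establish this. Names are removed, and supervising therapy is not the same as seeing every patient: glucose logs go to the coordinator and a dietitian supervises the diet. If it is the same person, blinding to clinical data would be hard to keep, since the investigator may adjust background diabetes drugs, handles adverse events and shares in data collection. The gap on visit order remains whoever reads.

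Finally, both arms follow a low-calorie diet aimed at about 5% weight loss, so a before-after change would not isolate a drug effect even with perfect masking. That is correct, and it is a further reason to rest the conclusion on the between-arm change.

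**Conclusion.** The point holds as a gap in the plan with a cheap remedy. Readers are blinded to clinical data, no masking of visit or reading order is provided, and the test named for EAT thickness is one that allocation blinding does not protect. The before-after false-positive rate is about 19% to 39% for a 0.5 mm shift and 8% to 13% for 0.25 mm, against a nominal 5%. These figures rest on assumed shifts, an assumed SD of change of 1.26 to 2.0 mm, 20 patients and no true change.

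Two stronger readings should be resisted. One is that readers will know the visit order: the documents are silent on this and do not say that scans are read unmasked. The other is that the trial's EAT result is invalid: a between-arm comparison of change is largely protected by the blinded placebo design, and EAT thickness is secondary.

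**What to change.** - Remove identifiers and dates from all clips. Have the two readers already planned read each patient's baseline and follow-up scans together, in random order, masked to visit and arm. Put this in the reliability section next to the present blinding sentence.
- State in advance which value is the endpoint: that of a reader not involved in patient care, or the mean of the two masked readings. Either is defensible. Both readings still serve the planned agreement analysis.
- Base the EAT conclusion on the between-arm comparison of change, adjusted for baseline thickness, and report the before-after test as descriptive. This matches the stated hypothesis.

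The cost is de-identifying files, holding baseline clips until the follow-up scan exists, and having results later. No extra reader or scan is needed. One limit remains: masked reading does not mask image acquisition, where beam and cursor orientation also matter.
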